Participants assigned to both groups will have: 1) reduced unmet needs, 2) reduced depressive symptoms, and 3) higher levels of satisfaction with care at 6 months than their baseline assessment values.

Caregivers assigned to CC+C will have greater reductions in caregiver burden at 6 months than those assigned to CC alone. Indicators of relationship strain (e.g., marital distress and/or mutuality) will show greater improvement in CC+C than CC at 6 months. 6 month gains in shared pleasant events, social engagement, and quality of life will also be greater in CC+C than in CC alone. 6-month desire to institutionalize will be lower in the CC+C group than those randomized to CC. Treatment engagement (e.g. action plan completion, attendance) is also predicted to be higher in the CC+C group than in CC.

For Aim 3, we anticipate that individuals who receive the CC+C intervention will have lower rates of placement in long-term care facilities at 6 and 12 months than those who receive CC alone. We also expect that behavioral problems will impact treatment outcomes such that those dyads with higher levels of behavioral disturbance at baseline will have greater change scores at 6 months. Spousal relationship to the veteran is also expected to moderate treatment outcome such that spousal caregivers are anticipated to have lower change scores compared to non-spousal caregivers across time; however, we expect this effect to be attenuated in the CC+C condition.

7. Background, including results of relevant research, gaps in the current knowledge.

Scope of the Problem

Over five million Americans are diagnosed with Alzheimer's disease or a related disorder (ADRD) and rates are expected to triple by 2050¹. It is the 6th leading cause of death in the United States and one in three older adults will have dementia when they die².

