10. Number of the subjects that will be recruited for study

At least seventy dyads (i.e. 70 veterans and 70 caregivers) will be recruited to achieve a final sample. However, caregivers can participate independently if the veteran is too impaired to participate meaningfully in the study.

11. Subject inclusion/selection criteria

Veterans:

- a. Must be age 19 or older
- b. Must have a diagnosis of dementia or a related disorder
- c. Must live in the community (i.e. not in a VA Community Living Center, nursing home, or other facility)
- d. Must cohabitatem with a caregiver;
- e. Must have reliable access to a telephone
- f. Must be willing to consent to participate or provide assent in conjunction with proxy consent if their decision-making capacity is compromised.

Caregivers:

- a. Must be age 19 or older
- b. Must self-identify as assisting with care for at least 8 hours/week
- c. Must be willing to consent to participate.

The study will include women and minorities and aim to represent the percentage reflected in Tuscaloosa VAMC medical care system (12% women, 44% minorities, and 1% Hispanic origin; though numbers of minorities might be slightly lower in the older cohorts targeted for this study as indicated above). No specific inclusion/exclusion criteria related to race/ethnicity are required.

12. Subject exclusion criteria

In addition to meeting the inclusion criteria outlined above, participants will be excluded in the following cases.

Veterans:

- a. Currently incarcerated
- b. Currently pregnant
- c. Dyads experiencing low levels of distress (as defined by a score of 0 or 1 on the Dementia Services Mini-Screen³², see below)

Note. Baseline or post-assessment interviews will be discontinued for Veterans experiencing severe cognitive impairment that would impair their ability to communicate during an interview, consistent with good clinical practices. However, they will not be excluded from participating in intervention sessions as appropriate and their available data (self-report or proxy report) will be retained for analyses.

Caregivers:

- a. Currently incarcerated
- b. Currently pregnant
- c. Experiencing severe cognitive impairment that would impair their ability to communicate during an interview
- d. Dyads experiencing low levels of distress (as defined by a score of 0 or 1 on the Dementia Services Mini-Screen³², see below)

13. Subject exit criteria

- a. Subjects will exit the study once one of the following conditions are met:

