- b. Completion of the study protocol
- c. Serious or life threatening adverse effects (including death)
- d. Withdrawal of consent by the Veteran or the Veteran's caregiver

14. Justification for use of special subject populations who may present informed consent issues (for example, incompetent patients, children, elderly, etc.) and reason for inclusion.

The study will not enroll prisoners, children, those who are terminally ill, or pregnant women. The study sample will include participants with varying degrees of cognitive impairment (from intact to severely impaired) and other mental health diagnoses (e.g., serious mental illness) that would classify them as vulnerable populations. In the event that these participants have impaired decision-making capacity, appropriate surrogate

consent will be obtained as described below. This vulnerable population is necessary to include in the current feasibility study to examine whether the intervention will ultimately be beneficial for this principal group. It is also possible that veterans over the age of 89 will be included in this research. However, veterans over the age of 89 will not be specifically targeted for enrollment.

15. Scientific and ethical justification for excluding classes (gender, race, etc.) of persons who might benefit from the research

No participant will be excluded from participation in the study on the basis of gender, race, ethnicity, socio-economic status, or physical disability.

16. Appropriateness of Impact of Study design on risk.

The risk of this study is low to minimal since it does not involve study medication or invasive procedures. Furthermore, all participants will receive an active treatment / intervention.

Minimal risks for veterans and their family members include:

- a. they may feel coerced to participate in interviews,
- b. they may feel uncomfortable, tired, or become bored during interviews,
- c. raw data from interviews may contain sensitive information that could cause embarrassment if it was obtained by others in an identifiable form.

It is unlikely that any discomfort or negative emotions will exceed those encountered as part of daily life. Interviews will be conducted separately for the veteran and their family member unless the veteran requests otherwise to increase privacy and minimize risk of embarrassment or discomfort. Given the benefits possible and minimal risks involved, the risk-benefit ratio for this study is favorable.

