17. Description of procedures to be performed.

The assessment schedule is summarized in Table 1 for screening (phone), baseline (in-person), 6-month assessment visit (in-person), and 12-month (phone) assessments. However, if a dyad prefers to complete the telephone assessments in person (e.g., while they are on station for another appointment), arrangements will be made to accommodate that request.

Table 1. Assessment Schedule

Measure (completed by Veteran or caregiver)	Admin. Time	S	B	6 mo	12 mo
Eligibility Screening (CG)	5m	X			
Dem Serv Mini-Screen (CG)	< 2m	X			
Subjective Stress/ Subjective Health (V, CG)	1m		X	X	X
Demographics (CG, CG*)	< 10m		X		
Health Literacy Screener (CG)	< 2m		X		
MoCA (V)	10m		X		

PSM IADL/ADL (CG*)	10-12m		X		
RMBPC (CG*)	5-10m		X	X	
CSDD (V, CG*)	10-20m		X	X	
Veteran QOL-AD (V, CG*)	5-10m		X	X	X
EuroQoL-5 Domain (V, CG*)	<5m		X	X	
Social Engagement (V, CG*)	<5m		X	X	
Dyadic Adj. Scale (V, CG)	5-10m		X	X	
Mutuality Scale (V, CG)	5m		X	X	X
Zarit Burden (CG)	< 5m		X	X	X
GAD-7 (CG)	< 5m		X	X	X
CES-D (CG)	5m		X	X	X
WHO-QOL-OLD (CG)	3m		X	X	
FFMQ (V, CG)	10m		X	X	X
Desire to Inst. (DTI) (CG)	<5m		X	X	X
NH Placement (EHR, CG)	<1m			X	X
Care Consultation Satisfaction Survey (CG)	<5m			X	
Caregiver Time Burden (min)			<130	<105	<50
Veteran Time Burden (min)			<80	<75	<30

Note. V = measures completed by veteran; CG = completed by caregiver; EHR = extracted from the electronic health record.

Screening

A HIPAA waiver for screening purposes will be obtained. Eligibility screening for interested dyads will typically occur over the telephone. If the Veteran and/or caregiver meets the inclusion criteria and do not meet exclusion criteria, a baseline assessment appointment will be scheduled. Informed consent procedures will be performed at baseline in accordance with the consensus recommendations for research with cognitively impaired populations developed by the Alzheimer's Association³³ and described in detail below. Proxy consent and participant assent will be collected when the participant is willing to assent for the study but is determined by the capacity assessment at the time of consent to be lacking capacity. Caregivers will also complete an informed consent. Veterans and their family caregivers will complete separate consent forms.

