Treatment delivery: The MSW-level interventionist will be trained to criterion and will be certified before administering the intervention. Accuracy of treatment delivery will be monitored. The interventionist will also complete a fidelity checklist to ensure that all treatment components are delivered during each session. As one measure of potential bias, the treatment fidelity checklist will include a self-reported item assessing the interventionists' desire/pressure to alter the randomly assigned condition for each dyad (i.e., agreement with the following statement will be assessed: "I believe the other arm of the study would have been a better fit for this dyad than the one they were randomly assigned"). Sessions will be audiotaped and 30% of sessions will be randomly selected and reviewed to ensure treatment fidelity to the CC and CC+C protocols. Treatment receipt: will be assessed by documenting the length of all intervention sessions (i.e., direct time spent with the dyads) and indirect time (e.g., documentation, case management, etc.). Participant knowledge of interventions components, which is sometimes included in measures of treatment receipt, is not appropriate for this study.¹¹⁰ Treatment enactment: will be monitored by: 1) the number of completed Action Plans and homework assignments in each group CC & CC+C, and 2) attendance/adherence to scheduled appointments. Other treatment implementation notes that do not directly impact human subjects protections include interventionists notes about "Process Considerations and Interventionist Pressures" including the interventionists' opinions about the two interventions (CC and CC+C).

18. Differentiation of "usual (standard) care" from research activities.

All procedures listed are voluntary in nature and unrelated to current clinical care. Participation in a similar clinical pilot program may be available to some families (e.g., those who live in rural areas may qualify for the Telephone Assisted Dementia Outreach Program, pending sustainment and availability which is unknown at the time this protocol is being submitted). However, no permanent services or "usual" treatment options similar to the one being studied are available at the Tuscaloosa VAMC.

19. Enlisting clinical expertise.

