Missing values are unavoidable in applied clinical intervention research. Where possible, variables to index the number and reasons for missing values will be documented. Based on the distribution of these missing value indices we may choose to eliminate some participants from the analyses ("list-wise deletion"). The extent that missing values are related to the independent (treatment group) or outcome variables will be assessed and if necessary controlled for statistically. Individuals who complete at least four sessions of the intervention (CC or CC+C) will be included in final analyses when time 2 data are available. Strict intention-to-treat methodologies are too conservative for this relatively small initial pilot study.

Data Analysis:

A series of one-way between subjects analyses of covariance (ANCOVAs) will be used to examine the main effect of “group” on 6 month variables of interest while controlling for values at baseline. The dependent variable in these analyses will be change scores with pre-treatment scores as the covariate. This analysis is statistically equivalent to ANCOVA with pre-treatment scores as the covariate and 6-month scores as the dependent variable, but it has an interpretational advantage in that the change scores represent an individual treatment effect (change during treatment). The change scores also represent the interaction term of a 2 (Group) X 2 (Time) repeated measures ANOVA. Consequently, when other covariates are added to the ANCOVAs to address treatment moderation effects, those covariate effects will be directly interpretable as moderator effects. That is, the added terms will assess the effects of the covariates on changes during treatment irrespective of Group (essentially a Time by Covariate interaction). When the interaction (multiplicative product) of covariate and Group is also added as another term in the ANCOVA, that interaction term will supply the moderating effect of the covariate on change during treatment as function of Group (i.e., differential effect of treatment as a function of the covariate).

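### The four-session entry rule filters observed 6-month scores on attendance, which the plan expects to differ by arm, and no as-assigned analysis of those scores is stated

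*Combined protocol and SAP*

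**What the plan says.** The entry rule is in Section 20, Treatment of Missing Values: "Individuals who complete at least four sessions of the intervention (CC or CC+C) will be included in final analyses when time 2 data are available". The reason follows directly: "Strict intention-to-treat methodologies are too conservative for this relatively small initial pilot study". The same paragraph offers one safeguard: "The extent that missing values are related to the independent (treatment group) or outcome variables will be assessed and if necessary controlled for statistically".

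Other sections bear on the rule:

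- **Section 6, hypotheses for Aims 2 and 3:** "Treatment engagement (e.g. action plan completion, attendance) is also predicted to be higher in the CC+C group than in CC".
- **Section 17, Treatment Implementation, Fidelity, and Process Variables:** treatment enactment is monitored partly through "attendance/adherence to scheduled appointments".
- **Section 13:** "Subjects will exit the study once one of the following conditions are met". The conditions are completing the protocol, serious or life-threatening adverse effects, and "Withdrawal of consent by the Veteran" or the caregiver. Low attendance is not listed.
- **Section 17, assessments:** "The assessment schedule is summarized in Table 1 for screening (phone), baseline (in-person), 6-month assessment visit (in-person), and 12-month (phone) assessments". Nothing there makes the 6-month visit depend on the number of sessions completed.
- **Section 20, Data Analysis:** each 6-month outcome is analysed by ANCOVA of change on group with baseline as covariate. Partial eta squared is the main indicator of treatment effect, and values of .01 or more are taken as possibly meaningful. No as-assigned or sensitivity analysis of the 6-month scores appears.

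**The concern.** Randomisation makes the arms comparable at entry. Selecting people for analysis on something that happens afterwards, and that the treatment is expected to change, gives up that comparability. Here the trial's own hypothesis is that one arm will attend more.

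The rule also bites on data in hand. Since low attendance does not end participation and the 6-month visit is not tied to sessions, someone with fewer than four sessions can have a 6-month score that the rule discards. The planned control for missing values does not reach these people, because their values are not missing.

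The effect sizes at stake are the trial's main evidence on preliminary effectiveness, and Section 32 says the data will support future grant proposals.

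Three related points are left open:

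1. Section 17 (Measures, item r) plans record review of placement after attrition, but Section 20 gives the placement regressions no analysis set.
2. Attendance is itself an outcome. If it were compared in the filtered set, everyone with fewer than four sessions would be cut from a comparison of attendance.
3. Dyads are randomised, but the rule speaks of individuals, so the unit for counting sessions is unclear. Under a per-person count, the rule would also need reconciling with the note in Section 12, which keeps the available data of severely impaired veterans.

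**Working it through.** **What the documents supply.** They do not give the share of participants expected below four sessions, in either arm. The recruitment figures (at least 70 dyads for 50 completers at 6 months, Section 20) allow a loss of 20/70 = 28.6%, but do not say how much of it is low attendance and how much is missing scores. The bias therefore cannot be calculated, only what it would take for it to matter.

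**Scope.** Table 1 rows marked at both baseline and 6 months: Subjective Stress/Health, RMBPC, CSDD, QOL-AD, EuroQoL-5, Social Engagement, Dyadic Adjustment, Mutuality, Zarit, GAD-7, CES-D, WHO-QOL-OLD, FFMQ and DTI. That is 14 rows, and the rule governs a 6-month ANCOVA on any of them.

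**The plan's threshold as a standardised difference.** With equal arms, partial eta squared of .01 corresponds to d = 2 × √(.01/.99) = 0.201. With 25 per arm and 47 error df, F = 47 × .01/.99 = 0.475, t = 0.689, and d = 0.689 × √(2/25) = 0.195.

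**Shift caused by the filter.** Assumptions: no true effect; among those with a 6-month score, shares p0 (CC) and p1 (CC+C) have fewer than four sessions; these low attenders lie g residual SDs below their own arm's baseline-adjusted mean. Removing them raises an arm's mean by g × p/(1 − p), so

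shift in (CC+C minus CC) = g × [p1/(1 − p1) − p0/(1 − p0)], positive meaning better in CC+C.

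| p0 (CC) | p1 (CC+C) | g = 0.5 | g = 1.0 |
|---|---|---|---|
| 10% | 10% | 0 | 0 |
| 10% | 5% | −0.029 | −0.058 |
| 20% | 5% | −0.099 | −0.197 |
| 30% | 5% | −0.188 | −0.376 |

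A simulated ANCOVA (baseline correlation 0.6, 2,000,000 per arm) gave −0.099 and −0.197 for the third row and −0.377 for the last row at g = 1.0. The unfiltered difference was 0.00.

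**Break-even.** Solve p0/(1 − p0) = 0.201/g + p1/(1 − p1).

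- p1 = 5%, g = 1.0: 0.201 + 0.0526 = 0.2536, so p0 = 0.2536/1.2536 = 20.2%.
- p1 = 5%, g = 0.5: 0.402 + 0.0526 = 0.4546, so p0 = 0.4546/1.4546 = 31.3%.
- p1 = 0: 16.7% and 28.7% (g = 1.0 and 0.5).
- p1 = 10%: 23.8% and 33.9%.

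**Meaning of g.** It is on the residual scale. With a baseline correlation of 0.6, a raw gap already present at baseline is multiplied by √(0.4/1.6) = 0.50, so g = 1.0 needs a stable raw gap of 2 SD. A gap that appears only after baseline is multiplied by 1/√(1 − 0.36) = 1.25, so g = 1.0 needs 0.8 SD.

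**A second model.** Let latent attendance correlate rho with the baseline-adjusted outcome, randomise 35 per arm (1:1 assumed), and retain the best attenders so that 50 remain. This attributes all 20 losses to the filter, so it is a severe case. Retaining 25 and 25 gives no bias. Retaining 60% in CC and 83% in CC+C (21 and 29) gives a spurious d of about 0.07, 0.10 and 0.18 at rho 0.2, 0.3 and 0.5. Retaining 51% and 91% (18 and 32) gives 0.12, 0.19 and 0.32. With positive rho the bias favours CC, the more heavily filtered arm.

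**The case against.** The rule is worded as a sufficient condition: it says who will be included, never that others are removed, and only strict intention-to-treat is declined. Exclusion is an inference. It is still the natural reading of the two sentences together. If it is not intended, the analysis set is undefined and needs the same correction.

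Higher average attendance in CC+C does not imply a different share below four sessions. This stands, and it is why no bias can be asserted. The arms may not be alike at that cut-off, however: CC+C carries about 6 to 8 sessions of counselling content, while no session count is given for CC.

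Early stoppers may often have no 6-month score, so the filter might remove little and missing scores could be the larger threat. This also stands as a possibility, and the proposed change does not cure bias from missing scores.

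The illustrated shifts are small beside sampling error. With 25 per arm the standard error of d is about √(2/25) = 0.28, and with 50 analysed the .01 threshold is crossed about 49% of the time with no effect and no bias. If more low attenders are removed from CC and they do worse, the shift goes against CC+C, so it would not manufacture the hypothesised benefit; if they do better, it would favour CC+C. These points limit the stakes, but sampling error is no reason to add an avoidable systematic error.

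The choice is openly stated and this is a pilot. That lowers the severity. It does not justify setting aside scores already collected. The three open points are requests for clarification and do not carry the main concern.

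**Conclusion.** The concern holds. The plan's wording makes a post-randomisation variable, predicted to differ by arm, a filter on observed 6-month scores, and it states no as-assigned analysis of them. Confidence in this reading is high.

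The size and direction of any bias cannot be determined from the documents. It is nil if the arms lose equal shares with equal prognosis. In the assumed modest case (10% against 5%) it is 0.03 to 0.06 residual SD, well under the plan's threshold. Reaching d of 0.20 takes roughly 20% to 31% of CC participants with scores below four sessions, against 5% in CC+C. The shares, g, rho and the baseline correlation are all assumptions. The figures show what the rule would need in order to matter, not that this is likely. The point should be fixed because the effect sizes are the trial's main indicator and the correction is cheap.

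**What to change.** In Section 20:

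- Define the primary set for the 6-month ANCOVAs as all randomised participants with a 6-month score, analysed as assigned whatever the number of sessions completed. Attempt the already scheduled 6-month assessment for those who stop sessions.
- Keep the four-session set as a labelled supportive analysis. State whether sessions are counted per person or per dyad, and report the numbers excluded by arm. If the count is per person, reconcile it with the note in Section 12.
- State that placement at 6 and 12 months is analysed in all randomised dyads, using the planned record review, and that attendance is compared in all randomised dyads.
- Report the number of missing 6-month scores and the reasons by arm, using the missing-value indices already planned. The change removes only the filter's bias; bias from missing scores can remain.

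The cost is SAP wording and possibly some follow-up effort, since the 6-month visit is in person by default. The documents do not say that assessments stop when sessions stop, so this effort may already be planned. Effects may look somewhat smaller once low attenders are included. The sponsor's preferred analysis is still reported.

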r. The 6-item **Desire to Institutionalize (DTI)** Scale⁵¹, which assesses the caregivers planning, thoughts, and actions about long-term care (LTC) placement over the past 6 months will be used to assess intentions to institutionalize their loved one. Six yes/no items (e.g., taken steps toward placement) are summed for a score of 0-6. Long-term care placement and/or hospitalization of the veteran (institutionalization) will be assessed using a single item rated either by the caregiver or via electronic health record review if the dyad is no longer enrolled in the study (e.g., due to attrition).

s. The 21-item **Care Consultation Satisfaction Survey** will be used to measure the participants' satisfaction with the Care Consultant and the Care Consultation services provided.

Once baseline data are collected, dyads will be randomly assigned to a condition (see interventions delivered below).

Randomization

Blocked randomization stratified by race and gender will be used to assign participants to either the: (a) CC group, or the (b) CC+C group. This two-group experimental design was chosen over other approaches (e.g., no comparison group designs, three-group design, cross-over design, etc.) because it most closely approximates the next level of clinical research (e.g., an efficacy study), which allows for the most directly applicable conclusions.

Interventions Delivered

1. Care Consultation (CC): is an established telephone-based, empowerment intervention that uses coaching and emotional support to mobilize family caregivers and individuals with dementia through psychoeducation, resource referral, psychosocial support, and encouragement of informal and formal service use utilization. A computerized clinical tool utilizing a password-protected VA-hosted website (i.e., operated within the VA server system) called the Care Consultation Information System (CCIS) guides the care consultant through a standardized delivery of protocol components, replacing a paper-based clinicians manual. Rather than a strong focus on assessment, this intervention is designed to quickly identify areas of unmet need through brief trigger questions called the “initial assessment” – much like an interview guide – which then immediately shapes development of concrete action plans.

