The study team has extensive clinical expertise in the delivery of interventions for individuals with dementia and their caregivers. See CVs and Bios uploaded and attached to this protocol for sample publications by the study team.

20. Description of the anticipated data and how the data will be analyzed to test the specific hypotheses results.

Study Design, Power, & Target Sample Size

We plan to recruit at least 70 dyads across the 3-5 year study period to ensure 50 completers at 6 months. This rate of 2 dyads per month is feasible given that there are 421 veterans with dementia currently receiving services from the TVAMC outpatient clinics (FY2013 clinical data). If 50% of them are in moderate to high distress (a conservative estimate based on our preliminary work), there would be over 200 individuals eligible. Power analyses were conducted to support this sample size (see attached grant text for more details).

Data Management and Analysis

Data Entry:

Data will be entered using Remark Office Optical Mark Recognition software and analyzed using Statistical Package for the Social Sciences (SPSS). Data analysis will be conducted using the VA Informatics and Computing Infrastructure (VINCI) server behind the VA firewall, as has been done for other TVAMC IRB approved studies. The research assistant will review all data for accuracy and will complete data tracking forms. A descriptive analysis of all assessment data will be conducted in order to examine distributional properties and correlations between the measures and the assumptions of statistical tests will be examined. Where necessary and sensible, data transformations, including the elimination of outliers, will be considered for variables with problematic properties.

Treatment of Missing Values:

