Outcome measures for caregivers will be run in separate analyses from those of the veterans with dementia, such that a series of ANCOVAs are anticipated for 1) self-report measures for the caregiver; 2) self-report measures for the veteran with dementia; and 3) proxy-reported measures for the veteran with dementia (as rated by their caregiver). Partial eta squared statistics of effect will be used as the primary indicator of likely treatment effects in this small sample. A large effect is indicated by a partial eta squared (hp^2) greater than or equal to 0.14, a medium effect is determined by a value greater than or equal to 0.06, and small effects are determined by values greater than or equal to 0.01. For the purposes of the current study, between groups effect sizes greater than or equal to .01 (a small effect) will be interpreted as potentially clinically meaningful in the interpretation of results since two active treatments are being compared. Cohen's d statistics will also be calculated for the purposes of the current feasibility study because they are one of the most common methods of estimating effect sizes and are more easily interpreted than the partial eta squared effects. In order to calculate Cohen's d statistics, standard error terms will be converted into standard deviations and used with the estimated marginal means from the post-treatment ANCOVAs. Both types of effect sizes will be calculated. Finally, logistic regression analyses will be conducted to determine if NH placement at 6 and 12 months is differentially related to treatment condition (i.e., group assignment) for individuals with dementia. NH placement (or not) will be the dependent variable in these analyses, and independent variables will include Group and relevant covariates.

21. Risks (physical, psychological, social, and economic) and steps taken to minimize these risks.

Physical Risks: There are no anticipated physical risks with this study. All activities in the study will be within the normal limits of participants' everyday physical demands. Increased veteran activity and/or range of motion could potentially result in exacerbation

of pre-existing pain conditions (e.g., arthritis, etc.); however, potential benefits in strength/decreased disability exceed potential risks.

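### The four-session and time 2 rule has no exemption for nursing home placement, so it excludes outcomes that the plan arranges to collect from dyads who leave early

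*Combined protocol and SAP*

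**What the plan says.** Section 17, Measures, item r, takes placement from the caregiver or "via electronic health record review if the dyad is no longer enrolled in the study (e.g., due to attrition". Table 1 in the same section schedules it at 6 and 12 months, with the health record and the caregiver as sources.

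Section 20, Treatment of Missing Values, sets the analysis population: those with at least four sessions of either intervention "will be included in final analyses when time 2 data are available". It adds the reason: "Strict intention-to-treat methodologies are too conservative for this relatively small initial pilot study". Time 2 is not defined; presumably it is the 6-month assessment.

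Section 20, Data Analysis, states that "logistic regression analyses will be conducted to determine if NH placement at 6 and 12 months is differentially related to treatment condition". It names the outcome, group and covariates, but no analysis set, and does not exempt placement from the rule above.

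On numbers, Section 20, Study Design, Power, & Target Sample Size, says: "We plan to recruit at least 70 dyads across the 3-5 year study period to ensure 50 completers at 6 months".

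**The concern.** The plan builds a follow-up route for leavers for this one outcome, then states an inclusion rule that many leavers cannot meet. For questionnaires, a missed 6-month visit means missing data. For placement, the record review can fill the gap, so the rule itself may remove a known outcome.

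Both conditions are determined after randomisation. Four sessions is an attendance threshold, and the Section 6 hypotheses predict higher attendance with CC+C than with CC. Placement may also be a reason to stop sessions or miss the 6-month visit. The placement comparison could therefore be made in groups that are no longer the randomised ones, and with fewer events. Because time 2 data is undefined, two analysts could also build different placement datasets from the same trial.

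**Working it through.** **The plan's own figure.** 70 recruited and 50 completers leave 20/70 = 28.6% not completing 6 months. The sample size cannot be reproduced, because alpha, power and effect size are left to grant text that is not in the documents.

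**Who is excluded, reading the sections together.**

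| Dyad | Placement status obtainable | In the final analyses as written |
|---|---|---|
| Fewer than four sessions | Yes, by record review if no longer enrolled | No |
| Four or more sessions, left before month 6 | Yes, by record review | No, if time 2 data means the 6-month assessment; yes, if a 6-month record status counts |
| Four or more sessions, left after a 6-month assessment | Yes, by record review at month 12 | Yes |

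The documents do not give the split between the first two rows.

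**Events lost (rates are assumptions).** Suppose all 20 non-completers are excluded, with placement rate p in completers and kp in leavers. Share lost = 20k/(20k + 50).
- k = 1: 20/70 = 29%
- k = 2: 40/90 = 44%
- k = 3: 60/110 = 55%

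At p = 10% these are 2 of 7, 4 of 9 and 6 of 11 events. If only 10 of the 20 are excluded, the shares for k = 1 and k = 2 halve to 10/70 = 14% and 20/90 = 22%.

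**Equal selection in both arms.** Assume 35 per arm and true placement of 25% (CC) and 12% (CC+C), so events = 8.75 + 4.2 = 12.95. Let q = 50% of placed dyads fail the rule in each arm. With 20 exclusions in total, unplaced dyads fail at q0 = (20 − 6.475)/57.05 = 23.7%.
- Analysed rate = p(1−q)/[p(1−q) + (1−p)(1−q0)]: 17.9% for CC and 8.2% for CC+C.
- Events fall from 12.95 to 6.5.
- SE(log OR), the square root of the summed reciprocal cells, rises from 0.65 to 0.89.
- Analysed odds = [p/(1−p)] × [(1−q)/(1−q0)]. The second factor is the same in both arms and cancels. The CC+C vs CC odds ratio is (0.12/0.88)/(0.25/0.75) = 0.41 before and after.

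With q = 70%, events fall to 3.9 and the SE rises to 1.12; the odds ratio is still 0.41.

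**Selection that differs by arm.** Keep the same rates, let 50% of placed CC dyads and 30% of placed CC+C dyads fail, and let unplaced dyads fail equally in both arms. The odds ratio becomes 0.41 × (0.70/0.50) = 0.57. In general it moves when retention of placed relative to unplaced dyads differs between arms. An attendance gap that changed retention of both by the same factor would leave it where it was.

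**The case against.** The strongest case against is that no sentence discards leavers' placement data. The inclusion rule does not say *only*, sits under missing values, and directly precedes the ANCOVAs. The restriction is also declared and explained, Aim 3 is exploratory, and its hypothesis is framed around receipt: "individuals who receive the CC+C intervention will have lower rates of placement in long-term care facilities at 6 and 12 months".

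Part of this stands. A reader might infer that placement data from all leavers are thrown away. The documents do not support that: exclusion is clear only below four sessions, depends on an undefined term for later leavers before month 6, and does not apply after a 6-month assessment.

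A reader might also take it as established that the rule removes events preferentially. It is plausible but assumed. Placement is not an exit criterion in Section 13, sessions are by telephone, and caregivers may take part without the veteran (Sections 10 and 23). Nor is the rule the only way status could be missing: consent may be withdrawn, the veteran may not be enrolled, and the documents do not say whether the record captures placements in non-VA facilities.

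The 20 of 70 is not the size of the exclusion either. Randomisation follows baseline, so some recruited dyads may be lost before it, and a completer is not defined as someone who passes the rule.

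The small-pilot reason does not answer the point. For placement the rule makes a small sample smaller. Framing the hypothesis around receipt does not define a population for the regression. It is true that the comparison stays imprecise with everyone included: for an assumed 30% vs 10%, two-sided 5% power is about 42% at 25 per arm and 55% at 35 per arm. That is no reason to omit outcomes already collected.

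**Conclusion.** The inconsistency is real and should be resolved before analysis. Followed as written, the plan excludes placement outcomes for dyads with fewer than four sessions, and possibly for all who leave before month 6. Up to 20 of 70 recruited dyads (29%) is an upper guide to how many. On assumed rates, the loss at that upper guide is 29% of events if leavers and completers are alike and 44% if leavers have twice the rate.

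A reader might infer that the falling placement rates in the equal-selection example show a biased treatment comparison. They do not for the planned analysis: the absolute rates are understated and precision falls, but the logistic odds ratio is unchanged. Bias in the odds ratio needs selection on placement that differs by arm. The predicted attendance difference makes that plausible, but its direction and size cannot be known from the documents. The shift from 0.41 to 0.57 is an illustration, not an estimate.

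**What to change.** Add to Section 20, under Treatment of Missing Values and Data Analysis, wording to this effect: *The four-session and time 2 conditions do not apply to placement. The 6- and 12-month placement analyses include every randomised veteran, by assigned arm, whose status is known from caregiver report or health record review. The number with known status is reported for each arm.* Define time 2 data in the same section for the other outcomes.

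The cost is a sentence or two of analysis wording; the record review is already planned. There are two downsides. Status may remain unknown for some veterans, for example after withdrawal of consent or where the veteran is not enrolled. The placement population will also differ from that of the questionnaire outcomes, which the report should state.
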